8.2.1. Inclusion Criteria

Patients must meet all of the following inclusion criteria to be eligible for enrollment into the study:

1. Age \geq 18 years or older.
2. Diagnosis of adenocarcinoma of the breast with evidence of metastatic disease or advanced disease not amenable to treatment with curative intent.
3. Documented HR+ (ER+ and/or PR+) tumor based on local standards.
4. Documented HER2- tumor based on local standards.
5. Physician has determined that treatment with palbociclib is indicated.
6. Evidence of a personally signed and dated informed consent document indicating that the patient has been informed of all pertinent aspects of the study.

7. Patients who in the opinion of the investigator are willing and able to comply with regular clinic visits as per standard of care practice at the site.

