2. Follow up through End of Study: Enter data at SOC visits where each subsequent (post palbociclib treatment) MBC treatment regimen is prescribed and at end of study.
3. Breast cancer treatment: including surgery, radiation, systemic chemotherapy, hormone therapy, and/or targeted therapy, in both neoadjuvant/adjuvant and metastatic disease settings, prior to, during, and post palbociclib treatment; supportive care is also collected in the metastatic setting while on this study.
4. Physician MBC Treatment Selection Survey: Treating physicians will complete a treating physician MBC treatment selection survey that will capture the reason(s) for treatment choice at start of palbociclib therapy and at start of subsequent therapies.
5. Clinical assessments: overall clinical response as judged by treating physician, at intervals per standard of care schedule: imaging assessment, clinical progression, and clinical biomarkers.

CCI

7. CBC: Baseline and during palbociclib treatment, enter any CBC during the 1st 3 cycles, then enter Day 1 (or prior to start of a new cycle) CBC for the subsequent cycles as per standard of care.

8. AE/SAE reporting begins at the time of the patient's first dose of palbociclib or the time of the patient's informed consent if s/he is already exposed to palbociclib and up to 28 calendar days following the last administration of palbociclib.

Table 2: EORTC QLQ-C30 and Geriatric Assessments

Data Collection and Entry	Baseline	Through End of Treatment with Palbociclib
	► SOC Visit 1	
EORTC QLQ-C30 ¹	x ¹	x ¹
G8 Screening Tool ²	x ²	x ²
ADL: Activities of Daily Living ²	x ²	x ²

ADL = Activities of Daily Living; EORTC QLQ-C30 = European Organisation for the Research and Treatment of Cancer Quality of Life Questionnaire Core 30

1. EORTC QLQ-C30 will be collected at baseline (before starting palbociclib) then monthly for the first 3 months of treatment with palbociclib, then every three months until the end of treatment with palbociclib.

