For safety events that are considered serious or that are identified in the far right column of the table above that are reportable to Pfizer within 24 hours of awareness, the investigator is obligated to pursue and to provide any additional information to Pfizer in accordance with this 24-hour timeframe. In addition, an investigator may be requested by Pfizer to obtain specific follow-up information in an expedited fashion. This information is more detailed than that recorded on the eCRF. In general, this will include a description of the adverse event in sufficient detail to allow for a complete medical assessment of the case and independent determination of possible causality. Any information relevant to the event, such as concomitant medications and illnesses must be provided. In the case of a patient death, a summary of available autopsy findings must be submitted as soon as possible to Pfizer or its designated representative.

Reporting period

For each patient, the safety event reporting period begins at the time of the patient's first dose of palbociclib or the time of the patient's informed consent if s/he is already exposed to palbociclib, and lasts through the end of the observation period of the study, which must include at least 28 calendar days following the last administration of a drug under study; a

report must be submitted to Pfizer Safety (or its designated representative) for any of the types of safety events listed in the table above occurring during this period.

If the investigator becomes aware of a SAE occurring at any time after completion of the study and s/he considers the SAE to be related to palbociclib, the SAE also must be reported to Pfizer Safety.

Causality assessment

The investigator is required to assess and record the causal relationship. For all AEs, sufficient information should be obtained by the investigator to determine the causality of each adverse event. For AEs with a causal relationship to palbociclib, follow-up by the investigator is required until the event and/or its sequelae resolve or stabilize at a level acceptable to the investigator, and Pfizer concurs with that assessment.

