4. Physician MBC Treatment Selection Survey: Treating physicians will complete a treating physician MBC treatment selection survey that will capture the reason(s) for treatment choice at start of palbociclib therapy and at start of subsequent therapies.

5. Clinical assessments: overall clinical response as judged by treating physician, at intervals per standard of care schedule: imaging assessment, clinical progression, and clinical biomarkers.

CCI

7. CBC: Baseline and during palbociclib treatment, enter any CBC during the 1st 3 cycles, then enter Day 1 (or prior to start of a new cycle) CBC for the subsequent cycles as per standard of care.

8. AE/SAE reporting begins at the time of the patient's first dose of palbociclib or the time of the patient's informed consent if s/he is already exposed to palbociclib and up to 28 calendar days following the last administration of palbociclib.

Table 2: EORTC QLQ-C30 and Geriatric Assessments

Data Collection and Entry	Baseline	Through End of Treatment with Palbociclib
	SOC Visit 1	
EORTC QLQ-C30 ¹	x ¹	x ¹
G8 Screening Tool ²	x ²	x ²
ADL: Activities of Daily Living ²	x ²	x ²

ADL = Activities of Daily Living; EORTC QLQ-C30 = European Organisation for the Research and Treatment of Cancer Quality of Life Questionnaire Core 30

1. EORTC QLQ-C30 will be collected at baseline (before starting palbociclib) then monthly for the first 3 months of treatment with palbociclib, then every three months until the end of treatment with palbociclib.

2. G8 Screening Tool and Activities of Daily Living to be completed only for patients equal to or greater than 70 years of age at the time of study enrollment. G8 and ADL will be collected at baseline (before starting palbociclib) then monthly for the first 3 months of treatment with palbociclib, then every three months until the end of treatment with palbociclib. ADL to be completed by the patient or in conjunction with the appropriately delegated site staff, G8 to be completed by the treating physician or the appropriately delegated site staff.

PFIZER CONFIDENTIAL

STUDY OBJECTIVES

The objectives of this prospective NIS of palbociclib in ABC treatment are:

- Palbociclib prescribing and treatment patterns in routine clinical practice in ABC treatment;
- Clinical outcomes;
- MBC treatment sequence prior to, during, and after palbociclib ;

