5 ANALYSIS SETS

FULL ANALYSIS SET

The full analysis set (FAS), also referred to as the Safety Analysis Set (SAS), or quality of life analysis set (QoLAS), is defined as all subjects enrolled in the study and received at least one dose of study medication. The FAS will be used in all analyses unless specified otherwise.

PER-PROTOCOL ANALYSIS SET

The per-protocol analysis set (PPAS) is a subset of the FAS and defined as all subjects enrolled in the study who a) received at least one dose of palbociclib, b) did not have any treatment-free interval (see Appendix 1 Data Derivation Details) and c) had no disease-free interval (see Appendix 1).

CCI

SUBGROUPS

Key measures, such as baseline patient characteristics, comorbidities, prior breast cancer treatments, treatment regimens during and after palbociclib treatment, and clinical outcomes will be assessed for the FAS and by specific subgroups defined by palbociclib hormonal partner and up to two additional subgroups. Patients will be classified into one of two or more levels for each subgroup of interest.

Potential subgroups of interest include:

- Age at enrolment (≥ 70 years / < 70 years)
- Ethnicity (Hispanic or Latino / Not Hispanic or Latino)
- Receipt of prior endocrine treatment (yes / no)
- Eastern Cooperative Oncology Group (ECOG) performance status (0-1 / 2-4)
- Insurance type (public / private / uninsured)
- ABC/MBC diagnosis at enrolment (de novo / recurrent disease)
- Disease stage at initial diagnosis (stage 0-IIIA / stage IIIB-IV)
- Charlson Comorbidity Index (CCI) (0 / 1-2 / 3+)

PFIZER CONFIDENTIAL

- Type of regimens (endocrine only / chemotherapy only / endocrine therapy combined with target therapy)
- Disease-free interval (0-<12 months / 12-<24 months / 24-<36 months / 36+ months)
- Visceral disease at enrolment (yes / no)
- Menopause status (yes / no)
- Line of therapy (LOT) in the ABC/MBC setting (1st line, ≥2nd line]

PFIZER CONFIDENTIAL

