Overall palbociclib treatment will be summarized as below for the FAS overall and by LOT:

- Number of cycles of palbociclib received
- Length of palbociclib treatment (months)
- Treatment disposition: (still receive palbociclib, discontinued palbociclib)

Palbociclib prescribing and treatment patterns will also be explored by cycle. For each cycle, below will be summarized:

- Starting dose (if less than 125mg, present reason)
- Primary reason for selecting palbociclib for the first cycle
- Dose modification (type, dose received after modification, reason)

Treatment patterns following enrollment will be reported, which include only lines started at enrollment:

- Type of therapy received (such as chemotherapy, hormonal therapy, other therapy)
- Agent (drug) composition of the treatment regimen received
- Time from initiation of treatment to initiation of each subsequent lines of treatment

- Time from discontinuation of previous line to initiation of the subsequent line of treatment
- Time from the start to end of each treatment line (in months for the total duration). This measure will be presented overall and by the top four regimens received in the line.

The sequence of agents/combination regimens received for first-line treatment in the ABC/MBC setting and subsequent lines of treatment will be presented. The proportion of all patients with each unique sequencing pattern will be reported for the overall study sample. Type of therapy sequencing (e.g., endocrine only, chemotherapy only, endocrine therapy combined with target therapy) will also be presented in the same format.

CLINICAL OUTCOMES

rwTR, rwPFS, and OS will be assessed by LOT (1st line, \geq 2nd line) in the ABC/MBC setting for the FAS. Based on the nonrandomized, observational nature of the study design, no clinical endpoints will be separately assessed and compared between specific treatment regimens.

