8.8.1 Adverse Events

All safety analyses will be completed following Pfizer safety analysis standards, including descriptive statistics on all safety endpoints for the FAS. AEs will be monitored throughout the study duration. If the type and/or number of AEs warrants further examination, interim analyses will be conducted to determine whether those experiencing AEs are systematically different from other study participants. If the percentage of patients withdrawing from the study exceeds 25%, interim analyses will be conducted to examine whether systematic differences exist between those withdrawing from the study and those that continue with palbociclib treatment. Descriptive statistics comparing women and men who complete follow-up with those who withdraw from the study will also be completed to determine whether there are any systematic (demographic, clinical) differences between these such defined groups.

Descriptive statistics will be presented for all AEs and will be examined by AE grade. The incidence of all-cause and treatment-related AEs and SAEs separately will be reported. Specifically, a summary of incidence will be presented for the following variables:

- Patients evaluable for AEs
- Number of AEs
- Patients with AEs

PFIZER CONFIDENTIAL

- Patients with SAEs
- Number of SAEs
- Patients with Grade 3 or 4 AEs
- Patients with Grade 5 AEs
- Patients permanently discontinued study associated with AEs
- Patients permanently discontinued study associated with SAEs
- Patients permanently discontinued treatment associated with AEs
- Patients permanently discontinued treatment associated with SAEs
- Patients temporarily discontinued treatment associated with AEs
- Patients temporarily discontinued treatment associated with SAEs
- Patients with dose reduction associated with AEs
- Patients with dose reduction associated with SAEs
- Deaths

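### AE recording starts at consent for patients already on palbociclib, but SAP 8.8.1 summarises AE incidence on all dosed patients without separating them

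*SAP*

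**What the plan says.** **Start of AE recording.** Protocol Section 10 says of safety event reporting that it "begins at the time of the patient's first dose of palbociclib or the time of the patient's informed consent if s/he is already exposed". Footnote 8 to Table 1, in both Protocol 8.3 and the SAP Introduction, gives the same two starts. For exposed patients it runs from "the time of the patient's informed consent if s/he is already exposed to palbociclib and up to 28 calendar days following the last administration". The footnote and Section 10 word the end of the window differently, which does not bear on this point.

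**Eligibility.** The treatment criterion in Protocol 8.2.1 is "Physician has determined that treatment with palbociclib is indicated". Neither 8.2.1 nor 8.2.2 excludes patients who have already started, and neither limits the time from first dose to consent.

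**Analysis.** SAP 8.8.1 plans safety summaries "including descriptive statistics on all safety endpoints for the FAS". SAP Section 5 defines the FAS, which is also the Safety Analysis Set, as "all subjects enrolled in the study and received at least one dose of study medication". The rows in 8.8.1 include patients with AEs, SAEs, Grade 3 or 4 AEs and AE-associated dose reductions. A row for patients evaluable for AEs is listed but not defined. SAP Section 8 (General Methods) calls for all summaries by hormonal-partner group as well as overall.

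**Neighbouring data.** For blood counts, Table 1 footnote 7 asks sites to "enter any CBC during the 1st 3 cycles", without reference to consent. Under Study Drug Exposure the SAP adds: "Palbociclib prescribing and treatment patterns will also be explored by cycle", with reasons for dose changes.

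**The concern.** A patient who had an AE in the first weeks of treatment, recovered and then consented contributes one person to the denominator and nothing to the numerator. The table treats that patient as event-free, when in fact the period was not observed.

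Three results are exposed: overall AE incidence, Grade 3–4 AE incidence, and the count of dose reductions linked to an AE. The last is affected because a reduction made for toxicity before consent may have no recorded AE to link to.

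There is also a comparison problem. If the already-exposed share differs between hormonal-partner groups or lines of therapy, AE percentages will differ between those columns even when toxicity is the same. A reader of a descriptive table has no means of seeing this, because the plan does not ask for the already-exposed share to be reported.

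**Working it through.** The plan states no figure for this effect, so there is none to reproduce. The check is a direct count.

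**Inputs**
- p, true incidence from first dose. The SAP Introduction and Protocol 6.2 cite Grade 3/4 neutropenia of 54% with letrozole and 62% with fulvestrant in the two phase 3 studies. These serve as reference values only.
- N = 1,500, the planned enrolment.
- f, the share of patients already exposed at consent. Not in the documents; assumed 5% to 30%.
- q, among already-exposed patients who have the event, the share whose event occurs only before consent. Not in the documents; assumed 0.25 to 0.75.

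**Formula.** Take p as equal in both groups and recording as complete once it starts.

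Recorded cases = N·p·(1 − f) + N·f·p·(1 − q) = N·p·(1 − f·q)

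Understatement of incidence = p·f·q

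**One case in full.** With f = 20%, 300 of 1,500 patients were already exposed. At p = 54%, 162 of them have the event. With q = 0.50, 81 of those are never recorded. True cases are 810 and recorded cases 729, so the table shows 48.6% instead of 54%.

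**Range at p = 54% (understatement in percentage points)**

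| f | q = 0.25 | q = 0.50 | q = 0.75 |
|---|---|---|---|
| 0% | 0 | 0 | 0 |
| 5% | 0.675 | 1.35 | 2.025 |
| 10% | 1.35 | 2.70 | 4.05 |
| 20% | 2.70 | 5.40 | 8.10 |
| 30% | 4.05 | 8.10 | 12.15 |

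At p = 62% and f = 20%, the same formula gives 3.1, 6.2 and 9.3 points.

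**Against sampling error.** The 95% half-width at p = 54% and N = 1,500 is 1.96 × √(0.54 × 0.46 / 1,500) = 0.0252, about 2.5 points. The bias exceeds this once f·q passes 0.0252 / 0.54, about 4.7%. At f = 10% that needs q above about 0.47; at f = 20%, above about 0.23. For p = 62% the half-width is about 2.46 points and the threshold is about 4.0%.

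**Between columns.** Two groups with equal toxicity but different shares differ by p·(f₁ − f₂)·q. With assumed shares of 30% and 10% and p = 54%, the gap is 0.54 × 0.20 × 0.25 = 2.7 points to 0.54 × 0.20 × 0.75 = 8.1 points.

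**What separate columns would show.** Patients observed from first dose would show 54%. Already-exposed patients would show p·(1 − q): 40.5% at q = 0.25 and 13.5% at q = 0.75.

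**The case against.** The strongest reply is that the already-exposed group may be small or empty. The questionnaires are scheduled before palbociclib starts, and the SAP baseline record is the last value before palbociclib, so much of the plan presumes enrolment before treatment. An AE that continues or recurs after consent may also still be recorded. Both points stand, and they are why the size is conditional. They do not remove the gap, because the reporting rule itself provides for patients already exposed.

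The denominator is also not settled. The AE-evaluable row might be meant to handle late entry, and 8.8.1 refers to sponsor safety standards that the reader cannot see. The FAS is the natural reading, since Section 5 makes it the default, but this counts as a missing definition and not as proof of a wrong denominator.

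Three stronger readings are tempting, and the documents do not support them.

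- *Early AEs cannot be matched to dosing and blood counts at all.* SAP 8.8.2 grades neutrophils from CBCs by cycle, independently of AE reports, and dose changes carry their own recorded reason. If CBCs from before consent are entered, laboratory neutropenia can still be set against dosing. What would be missing is the investigator-reported AE. In the other direction, no text says that pre-consent CBCs or dosing are back-entered. Charts are the source and the CBC footnote is not limited to post-consent samples, so back-entry is an inference.
- *SAP 8.9.6 pairs reported AEs with counts from the first month.* The time schedule there belongs to neutrophil means and medians. AEs of interest appear only in the lead-in, without timepoints, and the section is exploratory and deferred to a Documentation for Planned Analysis (DPA).
- *AE incidence is understated as a matter of fact.* That requires f and q both above zero, and the documents give neither.

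SAP Table 5 also lists neutropenia and anemia among conditions collected at enrolment. That may show an ongoing problem, but it does not enter the AE incidence rows.

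Finally, the study is descriptive, so replacing the FAS as the main AE population would be hard to justify for a subgroup of unknown size. That objection is accepted; the fix keeps the FAS.

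**Conclusion.** The point holds in conditional form. Recording starts late for already-exposed patients, the AE summaries include them through the FAS with no adjustment, and the AE-evaluable row is undefined. Any bias in AE, Grade 3–4 AE and AE-associated dose-reduction incidence is downward, and unequal already-exposed shares can produce differences between hormonal-partner or line-of-therapy columns.

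The size cannot be derived from the documents. For a 54% event it is about 0.7 to 12 points over f of 5–30% and q of 0.25–0.75, assuming equal true incidence in the two groups and complete recording after consent. It is zero if no patient was already exposed. CBC-graded neutropenia is less affected if pre-consent CBCs are entered, which is not stated. No figure in the plan is wrong on this account. This is a worthwhile, inexpensive improvement to the safety tables.

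**What to change.** In SAP 8.8.1:

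1. Keep the FAS table as planned.
2. Define the row for patients evaluable for AEs, stating how patients already exposed at consent are treated.
3. Report the number already exposed at consent and the time from first dose to consent, by hormonal partner and line of therapy.
4. Beside the FAS figure, show AE/SAE incidence in two further columns: patients whose consent is on or before first dose, and patients already exposed, with time at risk starting at consent for the latter.

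In the DPA for 8.9.6, limit any comparison that uses investigator-reported AEs to patient time after AE recording began. It would also help to state whether pre-consent CBC and dosing data are entered.

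The cost is SAP wording and one flag derived from the consent and first-dose dates. The SAP already relies on both: enrolment with consent defines its baseline date, and treatment initiation is the origin for rwPFS and OS. No visits or new data are needed and no patient is dropped. The downside is a smaller denominator, and so a wider interval, in the column observed from first dose.

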4 INTERIM ANALYSES

The study will consist of several interim analyses and a final analysis. The frequency and timing of the interim analyses will be driven by the observations and events available and also strategic medical interest (e.g., congress research submission deadlines). Each interim analysis will include data on baseline characteristics for patients enrolled in the study as well as longitudinal endpoints for patients with sufficient follow-up. Interim analyses will include summaries of patient, physician, and site characteristics. The specific measures (e.g., changes in patient-reported outcomes score, time-to-event analyses) presented for each interim analysis will be determined by Pfizer and analysis contributors based on the longitudinal data available at the time each interim dataset is released. At the time of each interim analysis, summaries related to treatment regimen, prescribing patterns, and dosing may be conducted as needed for abstracts and manuscripts provided sample sizes are sufficient for estimation.

PFIZER CONFIDENTIAL

5 ANALYSIS SETS

FULL ANALYSIS SET

The full analysis set (FAS), also referred to as the Safety Analysis Set (SAS), or quality of life analysis set (QoLAS), is defined as all subjects enrolled in the study and received at least one dose of study medication. The FAS will be used in all analyses unless specified otherwise.

PER-PROTOCOL ANALYSIS SET

The per-protocol analysis set (PPAS) is a subset of the FAS and defined as all subjects enrolled in the study who a) received at least one dose of palbociclib, b) did not have any treatment-free interval (see Appendix 1 Data Derivation Details) and c) had no disease-free interval (see Appendix 1).

CCI

SUBGROUPS

Key measures, such as baseline patient characteristics, comorbidities, prior breast cancer treatments, treatment regimens during and after palbociclib treatment, and clinical outcomes will be assessed for the FAS and by specific subgroups defined by palbociclib hormonal partner and up to two additional subgroups. Patients will be classified into one of two or more levels for each subgroup of interest.

Potential subgroups of interest include:

- Age at enrolment (≥ 70 years / < 70 years)
- Ethnicity (Hispanic or Latino / Not Hispanic or Latino)
- Receipt of prior endocrine treatment (yes / no)
- Eastern Cooperative Oncology Group (ECOG) performance status (0-1 / 2-4)
- Insurance type (public / private / uninsured)
- ABC/MBC diagnosis at enrolment (de novo / recurrent disease)
- Disease stage at initial diagnosis (stage 0-IIIA / stage IIIB-IV)
- Charlson Comorbidity Index (CCI) (0 / 1-2 / 3+)

PFIZER CONFIDENTIAL

- Type of regimens (endocrine only / chemotherapy only / endocrine therapy combined with target therapy)
- Disease-free interval (0-<12 months / 12-<24 months / 24-<36 months / 36+ months)
- Visceral disease at enrolment (yes / no)
- Menopause status (yes / no)
- Line of therapy (LOT) in the ABC/MBC setting (1st line, ≥2nd line]

PFIZER CONFIDENTIAL

